Blood (PD)			←-----	For sampling time points, see Section 9.7-----→						X		Additional 3HK and PD Biomarker samples may be collected other than those timepoints specified in Section 9.7 or on additional days based on emerging data

Procedure	Screening (within 28 days of Day 1)	Study Period (Days)								Follow-up (7-14 days following discharge)	Notes
		-1	1	2	3	4	5	6	7	8	
PGx Sample				X							Pre-dose if possible. Informed consent for optional genetics research must be obtained before collecting a sample
AE/SAE review			←	=====						→	X
Concomitant medication review	X	←	=====						→	X	

2.2. Part B & C – Cohorts 9, 10, 11, 12 & cohort 14, single bolus dose plus 7 day infusion, healthy volunteer subjects

Procedure	Screening (within 28 days of Day 0)	Study Period (Days)															Follow-up (Day 32 ± 2 days)	LFT Follow-up (Day 62 ± 2 days)	Notes
		-1	1	2	3	4	5	6	7	8	9	10	11	12	13	14	15		
Outpatient Visit	X																X	X	
Admission to Clinical Unit		X																	
Inpatient Stay at Clinical Unit		←	=====												→				
Discharge from Clinical Unit																	X		Following completion of all assessments
Informed consent	X																		
Inclusion and exclusion criteria	X	X																	

Procedure	Screening (within 28 days of Day 0)	Study Period (Days)															Follow- up (Day 32 ± 2 days)	LFT Follow- up (Day 62 ± 2 days)	Notes
		-1	1	2	3	4	5	6	7	8	9	10	11	12	13	14	15		
Demography	X																		
Full physical exam incl height and weight	X																		
Brief Physical		X															X	X	
Medical history (includes substance usage)	X																		Substances: Drugs, Alcohol, tobacco and caffeine
Clinical Safety Laboratory Assessments (HIV, Hep B and Hep C Screen at screening only ²)	X	X	X	X	X	X	X	X	X	X	X	X	X	X	X	X	X		Screening and day -1 safety labs must be in fasted state. ² If test otherwise performed within 3 months prior to first dose of study treatment, testing at screening is not required
LFTs (ALT, AST, AP, direct and indirect Bilirubin)	X	X	X	X	X	X	X	X	X	X	X	X	X	X	X	X	X		
cTnI / BNP	X	X	X	X		X			X		X		X		X		X		6hrs, 24hrs and 72hrs post dose. D7 immediately after end of infusion. D10, D13 and D15 anytime.
Urine Drug/Alcohol Breath Test	X	X															X ³	X ³	³ Alcohol Breath test only
FSH	X																		Females only, if required

Procedure	Screening (within 28 days of Day 0)	Study Period (Days)															Follow- up (Day 32 ± 2 days)	LFT Follow- up (Day 62 ± 2 days)	Notes

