		-1	1	2	3	4	5	6	7	8	9	10	11	12	13	14	15		
12-lead ECG	X	X	X	X	X	X	X	X	X	X	X	X	X	X	X	X	X		Triplicate ECGs will be obtained at screening and predose. Single measurements 30min and 6hr, 12hr, 24hr, and on Days 3-15 post-dose (equivalent to 36hr, 48hr, 72hr, 96hr, 120hr, 144hr, 168hr, 192hr, 216hr, 240hr, 264hr, 288hr, 312hr, 336hr, 360hr post-dose). ECG times may be adjusted once initial PK data is available.

Procedure	Screening (within 28 days of Day 0)	Study Period (Days)															Follow- up (Day 32 ± 2 days)	LFT Follow- up (Day 62 ±2 days)	Notes
		-1	1	2	3	4	5	6	7	8	9	10	11	12	13	14	15		
Continuous ECG Monitoring				X															Continuous monitoring from -1 hour pre-dose to 24hours post dose. Based on preclinical data levels of parent compound and tryptophan metabolites are expected to reach peak levels within a few hours of the start of dosing. A review of telemetry data will therefore be performed after 24 hours for clinically relevant alerts (see Appendix 9 for guidance). In the absence of such a signal, monitoring will revert to regular ECG assessments. In case clinically relevant changes are observed telemetry will be continued as long as deemed appropriate by the investigator. At the investigator's discretion and in consultation with the medical monitor telemetry could be reinitiated at any time during the study should any potential signals in regular ECG assessments emerge.
Transthoracic Echocardiogram	X																		Additional echocardiograms may be performed if increases in cTN or BNP are observed (see Section 8 for details), or at any time at the discretion of the investigator

Procedure	Screening (within 28 days of Day 0)	Study Period (Days)															Follow-up (Day 32 ± 2 days)	LFT Follow-up (Day 62 ± 2 days)	Notes
		-1	1	2	3	4	5	6	7	8	9	10	11	12	13	14	15		
Vital Signs	X	X	X	X	X	X	X	X	X	X	X	X	X	X	X	X	X		VS assessments will be performed in triplicate at screening and pre-dose. Single measurement at 30 min and 1 hr, 6hr, 24hr, and on Days 3-15 post-dose as outlined in Section 9.4.2. VS times may be adjusted based on initial PK data.
Columbia Suicide Severity Rating Scale (C-SSRS)	X	X			X			X									X		
Cognitive Assessments (6-CIT, fingertapping test and NPI)		X				X			X										
Study Treatment			←-----→																
Assessment of infusion site			←-----→																Up to 36 hrs post-start of infusion

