
Adverse effects due to reduction of 3 hydroxykynurenone (3HK) levels below the physiological range.
	
KMO deficient mice have undetectable levels of 3HK and elevation of metabolites, such as kynurenone (KYN), kynurenic acid (KYNA) and anthranilic acid (AA), but are viable and healthy. Robust increases in KYN, KYNA, AA and decreases in xanthurenic acid (XA) and quinolinic (QA) were measured in both rats and dogs in the 7-day dose range finding studies. Additionally a robust decrease in 3HK was observed in the dog study. 3HK levels could not be determined in the rat study. However the mid dose used in this rat study had previously been shown to reduce 3HK levels on the first day of dosing in a pharmacology study. Any adverse effects of changes in any of the TRP metabolites, including 3HK, would have been noted in these studies.
 
No information on the dynamics of the pathway after KMO inhibition in man is available and specific data on the rate of recovery of tryptophan metabolites, including 3HK, after
	
General safety monitoring will be conducted throughout the study, dose escalation criteria and stopping criteria (summarized in Appendix 3, Dose Escalation Committee), and a sentinel dosing approach (Section 5.1.1 and Section 5.1.2) have been outlined in the protocol.
 
Based on preliminary PK data from the initial two dose levels in Part A (SAD) a conservative safety observation period of 168 hours after single bolus infusion and after cessation of dosing in the 7-day continuous infusion study in a domiciled setting was chosen; 3HK data from humans is not available yet. The safety observation period will be reassessed based on emerging safety, PK and PD data during the trial.
 
Additional 3HK samples may be collected based on emerging data.

Potential Risk of Clinical Significance	Summary of Data/Rationale for Risk	Mitigation Strategy
	
treatment with GSK3335065 is not available from preclinical studies. Published studies with related KMO inhibitors have shown that recovery of metabolites typically occurs within 24-48hr after a bolus dose in rats (Mole et al 2016; Liddle et al, 2017 although 3HK itself was not measured in these studies.
	

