In cohort 14 participants will be given two 30 minute windows on Day 3 and Day 6 after completion of PK and PD collection in order to perform activities (i.e. shower) without having the canula inserted. These windows may be modified based on emerging safety and PK data.

Table 7 Study Duration of Cohort 13 (Part C)

Screening	All screening assessments to be completed within 28 days prior to the first dose.
Treatment Period	Each subject will take part in a single dosing session. Subjects will be in-house from the day prior to dosing until Day 8 post dose when they will be discharged after post dose assessments have been completed. Subjects will return as out-patients for any post-dose assessments.
Follow-up	Approximately 7-14 days after discharge from the unit. If warranted, additional follow-up visits may be scheduled.
Total Duration	Approximately 7 weeks

Table 8 Study Duration of Cohort 14 (Part C)

Screening	All screening assessments to be completed within 28 days prior to the first dose.
Treatment Period	During the study period subjects will be in-house from the day prior to dosing until Day 11 when they will be discharged after post-dose assessments have been completed. Subjects will return to the unit as out-patients for any post-dose assessments.
Follow-up	14 days after discharge following termination of study drug administration. If warranted, additional follow-up visits may be scheduled. Additional Liver Function Tests- 51 days after discharge
Total Duration	Approximately 13 weeks

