9.5. Pharmacokinetics

9.5.1. Blood Sample Collection

Blood samples for pharmacokinetic (PK) analysis of GSK3335065 in plasma will be collected at the time points indicated below. The actual date and time of each blood sample collection will be recorded. The timing of PK samples may be altered and/or PK samples may be obtained at additional time points to ensure thorough PK monitoring.

Processing, storage and shipping procedures are provided in the Study Reference Manual (SRM).

Part A (cohort 1 &2) and Part C (cohort 7):

1 mL of blood will be collected into Ethylenediaminetetraacetic acid (EDTA) tubes and processed to plasma for pharmacokinetic analysis, at the following time-points:

1 hr pre-dose, then 6 mins, 12 mins, 15 mins, 20 mins, 30 mins 1 hr, 2 hr, 3 hr, 6 hr, 9 hr, 12 hr, 15 hr, 18 hr, 24 hr, 30 hr, 36 hr, 42 hr, 48 hr, 60 hr and 72 hr post-dose.

Part A (cohort 3 - 8) and Part C (cohort 13):

1 mL of blood will be collected into EDTA tubes and processed to plasma for pharmacokinetic analysis, at the following time-points:

1 hr pre-dose, then 6 mins, 12 mins, 15 mins, 20 mins, 30 mins 1 hr, 2 hr, 3 hr, 6 hr, 9 hr, 12 hr, 15 hr, 18 hr, 24 hr, 30 hr, 36 hr, 42 hr, 48 hr, 60 hr, 72 hr, 84 hr, 96 hr, 108 hr, 120 hr, 132 hr, 144 hr, 156 hr, 168 hr post-dose.

Blood samples for PK analysis may also be taken during the follow up visit: approximately 7 to 14 days after subjects have left the unit.

Part B (cohort 9-12) & C (cohort 14):

2 mL of blood will be collected into EDTA tubes and processed to plasma for pharmacokinetic analysis, at all time-points specified below, except the ones in **bold**. These time-points will collect **4 mL** in EDTA tubes.

Study Day	PK sampling timepoint(s)
1	-1 hr, -30 mins, 6 mins, 15 mins, 30 mins, 1 hr, 2 hr, 3 hr, 4.5 hr, 6 hr, 9 hr, 12 hr, 18 hr .
2	Morning sample (around 08:00am) taken before first meal of the day
3-7	Morning sample (around 08:00am) taken before first meal of the day
8	Immediately after end of infusion, 6 hrs and 12 hrs following infusion termination
9	18 hrs, 24 hrs and 36 hrs following infusion termination
10	42 hrs, 48 hrs and 60 hrs following infusion termination
11	72 hrs, 84 hrs following infusion termination
12	96 hrs, 108 hrs following infusion termination
13	120 hrs, 132 hrs following infusion termination
14	144 hrs, 156 hrs following infusion termination
15	168 hrs following infusion termination

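### Table 8 discharges Cohort 14 on Day 11, 72 to 84 hours after the infusion ends, against the protocol's own 168-hour domiciled observation and Day 15 discharge

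*Protocol*

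**What the plan says.** Table 8 (Section 5.1.3) has Cohort 14 "in-house from the day prior to dosing until Day 11 when they will be discharged after post-dose assessments have been completed". It allows later out-patient returns, puts follow-up 14 days after discharge and puts the extra liver tests 51 days after discharge.

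Other current protocol text points to Day 15:

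- **Section 3.3.1**, on the risk of lowering 3HK, names a period of observation as mitigation: "168 hours after single bolus infusion and after cessation of dosing in the 7-day continuous infusion study in a domiciled setting was chosen". It makes no exception for women.
- **Section 2.2**, the schedule of activities, includes in its title "cohort 14, single bolus dose plus 7 day infusion, healthy volunteer subjects". Its day columns run to Day 15. The ECG note reads "Single measurements 30min and 6hr, 12hr, 24hr, and on Days 3-15 post-dose", and the vital-signs note likewise covers Days 3 to 15. Cardiac markers are due on "D10, D13 and D15 anytime". Follow-up is at Day 32 ± 2 and the liver visit at Day 62 ± 2.
- **Section 9.5.1** gives Cohort 14 the same PK schedule as Part B, ending with a 168-hour sample on Day 15. **Section 9.7** does the same for PD in Parts B and C, ending at 180 hours on Day 15.
- **The synopsis** says the Part C infusion cohort, under its old number 8, follows Part B. Part B subjects leave on Day 15 (Table 6; Section 5.4.2).

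**The concern.** Table 8 is an operative rule on how long volunteers stay under observation, and it conflicts with a named safety mitigation for the same regimen. If a site followed it, women given the infusion would go home on Day 11 while men given the same regimen would stay until Day 15. Out-patient visits could recover the scheduled samples, but not continuous residence in the unit. The protocol also reports that the half-life proved much longer than predicted (Section 5.4.1), and that finding underlies the 168-hour period.

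**Working it through.** **Inputs**

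- Infusion length: 7 days from Day 1, so 7 × 24 = 168 h.
- End of infusion: Day 8, where Section 9.5.1 lists "Immediately after end of infusion, 6 hrs and 12 hrs following infusion termination".
- Preliminary half-life: about 35 h (Section 9.3).
- Allocation in Cohort 14: 6 active, 2 placebo (Section 5.1.3).

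**Step 1. Reproduce the plan's own figure.** Hours from the end of infusion to the start of Day d are (d − 8) × 24. For Day 15 this is 7 × 24 = 168 h, which agrees with Sections 3.3.1 and 9.5.1. The single-bolus female cohort (Table 7) also agrees: dosing on Day 1 and discharge on Day 8 is 7 × 24 = 168 h.

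**Step 2. Table 8.** For Day 11, (11 − 8) × 24 = 72 h. Section 9.5.1 also puts an 84 h sample on Day 11, so discharge after that sample is at 84 h. The shortfall is 168 − 72 = 96 h, or 168 − 84 = 84 h.

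The cardiac-marker note in Schedule 2.2 instead places the end of infusion on Day 7. Taking that literally gives (11 − 7) × 24 = 96 h, still 72 h short. Day 8 is better supported, by the 168 h infusion length and by Section 9.5.1.

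**Step 3. Drug remaining at discharge.** The fraction left is 0.5^(t / half-life), assuming mono-exponential decay. The 24 h and 48 h half-lives are assumed, to show a range.

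| Time after infusion | 24 h | 35 h | 48 h |
|---|---|---|---|
| 72 h | 12.5% | 24.0% | 35.4% |
| 84 h | 8.8% | 18.9% | 29.7% |
| 168 h | 0.8% | 3.6% | 8.8% |

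At 35 h, the half-lives elapsed are 72/35 = 2.06, 84/35 = 2.40 and 168/35 = 4.80.

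**Step 4. Assessments after discharge.**

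| | Total post-infusion | After 72 h | After 84 h |
|---|---|---|---|
| PK times (9.5.1) | 18 | 8 | 7 |
| PD times (9.7) | 18 | 9 | 8 |

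The ECG and vital-sign checks on Days 12, 13, 14 and 15, and the cardiac markers on Days 13 and 15, also fall after a Day 11 discharge.

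**Step 5. Follow-up dates.** The schedule windows are Days 30 to 34 for follow-up and Days 60 to 64 for the liver visit.

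| Offset after discharge | From Day 11 (Table 8) | From Day 15 (Table 6) |
|---|---|---|
| 14 days | Day 25, 5 days early | Day 29, 1 day early |
| 51 days | Day 62, inside | Day 66, 2 days late |

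The 51-day offset fits only a Day 11 discharge, which suggests that Day 11 and the 51 days are left from an earlier schedule. The offsets that match the schedule from Day 15 are 32 − 15 = 17 days and 62 − 15 = 47 days.

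**The case against.** The strongest reply is that this is a stale table cell and that other text would stop it doing harm. Section 9 makes adherence to the schedule of activities mandatory. Twelve-hourly sampling through Day 14 is hard to run on discharged volunteers, so a site would probably notice the conflict when planning visits. Table 8 provides for out-patient returns, so the assessments in Step 4 would move rather than be lost. The 168 h period was itself provisional: Section 3.3.1 says it will be reassessed as data emerge, and Section 5.1.3 lists it among the items to review before Part C. The study was terminated after sentinel dosing in Part A Cohort 3 (SAP Section 1), so nobody in Cohort 14 was dosed and no analysis depends on Table 8.

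Most of this stands, and it keeps the practical weight low. It does not remove the contradiction. Collecting every scheduled sample from out-patients would still give up the domiciled stay. The review before Part C could change the period, but nothing in the current text sets it at Day 11 or gives a reason for doing so.

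Two cautions also stand. Some columns of Schedule 2.2 are displaced in the text available to me, so the Day 15 discharge does not rest on that table's discharge mark alone; Table 6 and Sections 3.3.1, 5.4.2 and 9.5.1 support it independently. The residual-drug percentages describe exposure at discharge and are not an estimate of harm.

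**Conclusion.** The point holds. Table 8 is wrong as written: it gives 72 to 84 h of domiciled observation after the infusion where the protocol elsewhere requires 168 h, a shortfall of 84 to 96 h for 8 women. At a half-life of 35 h, the 6 on active drug would leave with about 19% to 24% of the end-of-infusion level, against 3.6% at 168 h. Those percentages rest on a preliminary half-life and mono-exponential decay; the shortfall itself rests only on calendar arithmetic with the infusion ending on Day 8. This is an internal inconsistency in a safety rule that should be corrected. The likely harm is low, and there was no effect on this study's results.

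**What to change.** In Table 8, replace Day 11 with Day 15. State follow-up as Day 32 ± 2 and the liver visit as Day 62 ± 2, which are 17 and 47 days after discharge. Make the same two follow-up corrections in Table 6, where the present offsets of about 14 and 51 days give Days 29 and 66.

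If a stay shorter than 168 h were really wanted for Cohort 14, the protocol should say so, give the reason, and change Section 3.3.1 and Schedule 2.2 to match.

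The cost is protocol wording only, and it could go into any amendment made at the review before Part C. It adds no night, visit or sample beyond what Schedule 2.2 already requires.

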5.2. Number of Participants

Sufficient subjects will be randomised to achieve 112 evaluable subjects (Part A: 64 healthy male subjects, Part B: 32 healthy male subjects, Part C; 16 WONCBP (8 subjects for Cohort 13, 8 subjects for Cohort 14). If subjects drop out early or lost to follow up, additional subjects may be enrolled as replacement subjects and assigned to the same treatment sequence following Sponsor approval, in order to ensure an adequate number of subjects are evaluable..

5.3. Participant and Study Completion

A participant is considered to have completed the study if he/she has completed all phases of the study including last scheduled procedure shown in the Schedule of Activities.

A subject who receives an active dose of study medication and for whom a pharmacokinetic specimens have been collected will be considered an evaluable subject for assessing the pharmacokinetics.

[figure not shown]
The end of the study is defined as the date of the last visit of the last participant in the study.

5.4. Dose Justification

5.4.1. Starting dose for Part A

[figure not shown]
Inhibition of KMO in pre-clinical species results not only in a decrease in the rate of formation of 3HK, but also in an accumulation of KYN. This increase in KYN works to oppose the inhibition of KMO by increasing flux through the pathway. In rats, the maximal steady state change in KYN observed following KMO inhibition was between 6 and 10-fold, while in mice deficient in KMO the baseline KYN level was 19 times higher than in wild type animals (Mole et al, 2016). The magnitude of increase in KYN that will be observed in humans is not known so it is not possible to predict exactly what level of 3HK reduction will be observed at any given drug level. Instead modelling has been used to establish an appropriate dose range to cover a range of potential human scenarios (2 fold to 20-fold increase in KYN).

A model was developed to simulate the clinical doses according to the range increase in KYN previously mentioned and for different degrees of 3HK inhibition. The model utilised the PK preclinical parameters that were scaled to the human counterparts. More specifically, the volume of distribution (V) was predicted from the mean of rat and dog volumes, giving a value of 0.39 L/kg (27 L). Prediction of human clearance (CL) was undertaken using scaling from rat and dog with the method of exponents. Similar values were obtained using methods either restricted (2.9 L/hr) or non restricted (1.9 L/hr) by plasma protein binding so subsequent dose estimates use the mean of these values (2.4 L/hr). Finally, the half-life is predicted to be 7.8 h.

To set the starting dose minimum anticipated biological effect level (MABEL), it was first assumed that the magnitude of the maximal KYN change observed in man following KMO inhibition will be substantially smaller than in the rat (2 fold compared to 6-10 fold), thus making the pathway more sensitive to inhibition. Under these circumstances, a dose targeting 0.2 times the cellular Ki would decrease 3HK levels by no more than 10-20 % while having no measurable impact on KYN levels. In contrast, if the magnitude of the maximal change in KYN in man is assumed to be substantially higher than in the rat (20 fold compared 6-10 fold), then a dose targeting 0.2 times the cellular Ki would be predicted to have no measurable effect on either 3HK or KYN levels. This has therefore

been selected as the MABEL dose. The figure below depicts the predicted PK profile for the MABEL dose.

In accordance with FDA guidance, the maximum recommended starting dose (MRSD) is 1/10th (applying the default safety factor) the NOAEL human equivalent dose (HED) in the more sensitive or more relevant preclinical species, correcting for body surface area between species. For GSK3335065 the more sensitive species is the rat as in the rat the lowest HED can be identified. The safety factor may be adjusted depending on the expected pharmacology, toxicology, and preclinical pharmacokinetics of the drug candidate, or previous experience with compounds in the same pharmacologic/structural class. As this is a novel mechanism a more conservative safety factor of 100 to calculate the MRSD was used.

Using the data from the 2 week Good laboratory practices (GLP) toxicity studies in rat, the MRSD was estimated to be 16 mg based on the following calculations:

$140 \text{ mg/kg/day} / 6.2 = 22.6 \text{ mg/kg} / 100 = 0.226 \text{ mg/kg}$; for a 70 kg human the MRSD is ~ 16mg. Hence, the proposed 0.1 mg MABEL starting dose is approximately 160-fold below the MRSD of 16 mg.

The planned doses and predicted exposures compared to the 2 week GLP study in rats are shown in [Table 9](#) below.

Table 9 Part A Planned doses, predicted exposures, and anticipated margins to rat NOAELs

	Dose	Predicted Cmax (fold Ki) (μ g/ml)	Margin to NOAEL (Cmax)	Predicted AUC (0-24h) (μ g.hr.mL ⁻¹)	Margin to NOAEL (AUC 0-24h)
Cohort 1, Period 1	0.1 mg IV bolus	0.004 (0.2xKi)	39750	0.036	46667
Cohort 2, Period 1	0.25 mg IV bolus	0.01 (1xKi)	15900	0.091	18462
To facilitate subject recruitment, the study design will be changed to a parallel cohort design (Amendment 3).					
Cohort 3	1.3 mg IV bolus	0.05 (5xKi)	3180	0.481	3493
Cohort 4	2.6 mg IV bolus	0.1 (10xKi)	1590	0.944	1780
Cohort 5	5.5 mg IV bolus	0.2 (20xKi)	795	2.020	832
Cohort 6	12 mg IV bolus	0.46 (50xKi)	346	4.398	382
Cohort 7	35 mg IV bolus	1.37 (150xKi)	116	12.753	132
Cohort 8	54 mg IV bolus	2.0 (220xKi)	80	22.4	75

Dose Escalation Approach in Part A

The decision to proceed to the next dose level will be based on safety and tolerability data obtained up to 8 days post dose (at discharge from clinical unit) from at least 6 subjects at the prior dose level. The review data set will at a minimum consist of the listings of any adverse events, flagged vital signs, flagged findings during the cardiac monitoring (telemetry) ECG, flagged findings in 12-lead ECGs and laboratory findings (including LFTs, cardiac troponin [cTN], BNP). Available PK data from the prior dose level, together with any available PD data will also be reviewed.

Preliminary PK Data

Estimates of the systemic exposure over 24 hours post-dose, from Part A, Cohorts 1 and 2, were generally consistent with predictions. However, the apparent half-life was significantly longer than the 7.8 hours that had been predicted. Consequently, the PK sampling regimen has been extended to capture the longer terminal phase of elimination.

Preliminary PD Data

Preliminary PD data from Part A to measure the effects of KMO enzyme inhibition showed wide variability in biomarker plasma concentrations both at baseline and during treatment, and included the following biomarkers of the tryptophan pathway: Kynurenine (Kyn), 3-hydroxykynurene (3-HK), tryptophan, kynurenic acid, anthranilic acid, 3-hydroxyanthranilic acid, quinolic acid and xanthurenic acid. To enable a reliable assessment of baseline levels and their underlying variability, as well as to ensure all

subjects are in a similar physiological state upon receiving the dose allowing time for any uncontrolled external influences on biomarker levels (food intake, meal time, sleep cycle) to dissipate, subjects will be enrolled at least 12 hours prior to dosing, eg. the afternoon of the day prior to the dose. Blood samples for the measurement of tryptophan pathway biomarkers will be taken regularly. Sleep disruption will be avoided, as it may perturb biomarker levels from their natural levels. On the day prior to dosing (day -1), the proposed sample times are as follows: -16hrs, -14hrs, -12hrs and 10hrs followed by -2hrs and approximately 0.5hrs predose on the day of dosing. (day 1). Flexibility around these nominal times will be permitted.

Highest Dose in Part A

The highest dose planned in Part A is a 54 mg dose with an expected exposure margin in terms of AUC to the rat NOAEL of 75-fold. Higher doses may be administered if exposures are lower than predicted but the maximum exposure will not exceed the 75-fold exposure margin in terms of AUC to the rat NOAEL.

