5.4.3. Maximum dose/exposure in Part B

The highest dose planned to be explored will target a concentration just over 100 times the Ki in PART B. Modelling suggests that the highest anticipated dose (73.4 mg total dose on day 1 followed by 50.4 mg/day on days 2-7) should achieve reductions of 3HK in excess of 90% even if the increase in KYN observed is substantially larger than that seen in the rat (20 fold compared to 6-10 fold). This value remains below (177-fold for Cmax and 75-fold for AUC(0-24h)) the plasma concentration at the NOAEL in the toxicity studies in rats and dogs. The highest dose also remains below the threshold for increased drug induced liver injury (DILI) risk (100 mg). Higher doses may be administered if exposures are lower than predicted but the maximum exposure will not exceed the 75-fold exposure margin in terms of AUC to the NOAEL.

This dose is anticipated to reduce 3HK levels by >90%. Preclinical data support that lowering 3HK levels through KMO inhibition >90% in humans is anticipated to be safe as KMO deficient mice have undetectable levels of 3HK and elevation of metabolites, such as kynureneine (KYN), kynurenic acid (KYNA) and anthranilic acid (AA), but appear viable and healthy. A robust decrease in 3HK of >90% was observed in the dog 7-day dose range finding study. 3HK levels could not be determined in the rat study. However the mid dose used in this rat study had previously been shown to reduce 3HK levels by ~85% on the first day of dosing in a pharmacology study. Any adverse effects of changes in 3HK would have been noted in these studies.

Table 10 Part B planned doses, predicted exposures, and anticipated margins to rat NOAEL. 4 ascending doses are planned in Part B.

	Dose range IVB & IV infusion	Expected (%) KMO inhibition	Targeted Concentration (Cmax) (ug/ml)	Margin to NOAEL (Cmax)	AUC(0-168h) (ug.hr.mL ⁻¹)	Margin to NOAEL (AUC 0-24h)
Anticipated starting dose	IVB 0.14 mg + IV Inf. 0.012 mg/h	25%	0.005 (0.6xKi)	31800	0.9	13067
Anticipated pharmacologically active dose	IVB 7.5 mg + IV Inf. 0.63 mg/h	>60%	0.27 (30xKi)	589	47	250
Anticipated pharmacologically active dose	IVB 12 mg + IV Inf. 1.1 mg/h	>85%	0.45 (50xKi)	353	85	138
Highest anticipated dose	IVB 23 mg + IV Inf. 2.1 mg/h	>90%	0.9 (100xKi)	177	156	75

5.4.4. Part C:

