9.3. Treatment of Overdose

For this study, any dose of GSK3335065 greater than the agreed dose for a particular cohort, dosing session or study part will be considered as an overdose.

GSK does not recommend specific treatment for an overdose

In the event of an overdose the investigator or treating physician should:

1. Contact the Medical Monitor immediately
2. Closely monitor the subject for adverse events (AEs)/serious adverse events (SAEs) and laboratory abnormalities until GSK3335065 can no longer be detected systemically (at least 8 days which is equivalent to 5 times the observed preliminary half life of ~35 hours for GSK3335065).
3. Obtain a plasma sample for pharmacokinetic (PK) analysis within 1 days from the date of the last dose of study treatment if requested by the Medical Monitor (determined on a case-by-case basis)

4. Document the quantity of the excess dose as well as the duration of the overdosing in the CRF.

Decisions regarding dose interruptions or modifications will be made by the investigator in consultation with the Medical Monitor based on the clinical evaluation of the subject.

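### The 75-fold AUC margin printed for the top Part B regimen rests on a predicted 7.8 h half-life and is not supported by the preliminary half-life of about 35 h

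*Protocol*

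**What the plan says.** Protocol Section 5.4.1 scales human PK from rat and dog: volume 27 L, clearance 2.4 L/h, and "the half-life is predicted to be 7.8 h". Under the preliminary PK results from Cohorts 1 and 2, the same section says that exposure over 24 h was broadly in line with prediction but that "the apparent half-life was significantly longer than the 7.8 hours that had been predicted". Section 9.3 gives the value, basing overdose follow-up on "5 times the observed preliminary half life of ~35 hours for GSK3335065". The stated responses to the preliminary PK are longer PK sampling (Section 5.4.1), a 168 h observation period (risk table, Section 3.3.1) and the overdose follow-up.

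Table 9 (Part A, top dose 54 mg) and Table 10 (Part B, top regimen 23 mg bolus plus 2.1 mg/h for 7 days) each print an AUC margin to the rat NOAEL of 75 in the top row. Both margin columns are headed as AUC over 0-24 h. Section 5.4.3 says of Part B that "the maximum exposure will not exceed the 75-fold exposure margin in terms of AUC to the NOAEL"; Sections 5.4.1 and 7.2 and Appendix 3 repeat this limit. The risk table cites the 75-fold figure as mitigation for the cardiac, liver, haematological and inflammatory findings, and 177-fold on concentration for the cardiac finding.

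The Part B schedule (Section 2.2) supports 24 h of continuous ECG monitoring with the statement that parent and metabolite levels are "expected to reach peak levels within a few hours of the start of dosing".

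**The concern.** If the AUC over the first 24 h after a bolus is as predicted but the later decline is much slower, more AUC lies beyond 24 h. Total AUC per mg is then larger and clearance smaller. This changes little over the first day of a single dose. Over a 7-day constant infusion, concentrations go on rising past the predicted plateau.

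The top Part B row sits exactly on the cap, so it has no room to absorb a lower clearance. A reader of the risk table or Section 5.4.3 takes 75-fold as the current margin for the planned top exposure. The preliminary PK in the same document gives reason to doubt it.

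**Working it through.** **Inputs.** CL 2.4 L/h, V 27 L and predicted half-life 7.8 h (Section 5.4.1); observed half-life about 35 h (Section 9.3); 24 h AUC as predicted (Section 5.4.1); regimens and margins from Tables 9 and 10. The NOAEL AUC(0-24h) is not printed. Back-calculated from Table 9 as AUC × margin it is 0.036 × 46667 = 1680 µg·h/mL, and every row gives 1680 to 1683.

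**1. Reproducing the printed figures**
- Half-life: ln2 × 27/2.4 = 7.8 h.
- AUC(0-24h) per mg: (1 − e^(−24×2.4/27))/2.4 = 0.367. This reproduces Table 9 within 2% from 0.1 to 35 mg.
- 54 mg row: 54 × 0.367 = 19.8, margin 1680/19.8 = 85. The printed 22.4 instead matches dose/CL = 54/2.4 = 22.5, which is AUC(0-∞), margin 75.
- Top Part B row: total dose/CL = (23 + 2.1 × 168)/2.4 = 156.6 (printed 156). Then 156/7 = 22.3 and 1680/22.3 = 75. Integrating only to 168 h gives 147, margin 80.

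Both printed 75s therefore follow from CL 2.4 L/h.

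**2. Which 35 h models fit the reported 24 h exposure?** Let k = ln2/35 = 0.0198 per h.
- Keep V = 27 L: CL 0.535, and 54 mg gives AUC(0-24h) 38.2, 93% above prediction. Excluded.
- Keep CL = 2.4 L/h: AUC(0-24h) 8.5, 57% below prediction. Excluded.
- Match AUC(0-24h): CL = (1 − e^(−24k))/0.367 = 1.03 L/h, V = 1.03/k = 52 L. Retained.

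**3. Top Part B regimen, matched one-compartment model**
- AUC(0-168h) = (23/CL)(1 − e^(−168k)) + (2.1/CL)[168 − (1 − e^(−168k))/k] = 21.5 + 243.3 = 265, against 156 printed. Seven-day average margin: 1680/(265/7) = 44.
- Last-day AUC 47.2: margin 36.
- Concentration about 1.05 µg/mL at 24 h and 1.98 at 168 h (ratio 1.9), against a target Cmax of 0.9. The NOAEL Cmax implied by Table 10 is 0.9 × 177 = 159, so the Cmax margin would be 159/1.98 = 80, not 177.

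**4. Predicted profile to 24 h, then a 35 h tail.** C(24) per mg = e^(−24×2.4/27)/27 = 0.00439. Tail AUC = 0.00439/k = 0.2215. Total 0.367 + 0.2215 = 0.589, so CL = 1.70. Steady-state level 2.1/1.70 = 1.24; margin 1680/(24 × 1.24) = about 57.

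**5. Biexponential sensitivity.** Initial concentration dose/27, terminal half-life 35 h, fast phase solved to keep AUC(0-24h) as predicted, slow-phase share f of initial concentration varied:

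| f | CL (L/h) | 7-day average margin | Last-day margin |
|---|---|---|---|
| 2% | 2.30 | 78 | 77 |
| 3% | 2.25 | 77 | 75 |
| 5% | 2.16 | 75 | 73 |
| 10% | 1.96 | 71 | 66 |
| 20% | 1.63 | 63 | 56 |
| 50% | 1.05 | 45 | 36 |

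The one-compartment case is the limit of this family, at f = 27/52 = 52%. As a cross-check, a steady-state margin of 75 needs CL of at least 75 × 24 × 2.1/1680 = 2.25 L/h, only 6% below 2.4.

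**6. Part A, 54 mg.** On AUC(0-24h) the margin is unaffected, because that exposure matched prediction. On AUC(0-∞), which the printed 22.4 resembles, it becomes 1680 × 1.03/54 = 32 (step 3 model) to 1680 × 1.70/54 = 53 (step 4 model).

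**The case against.** The 75-fold figure is a cap on exposure as well as a prediction. Section 5.1.1 holds Part A within it using emerging PK, Section 10.3.3 overlays observed PK on the model at each review, and Section 7.2 lets doses move in either direction within the cap. Part B doses are offered as a guide, and an all-data review with possible amendment comes first (Section 5.4.2). The 35 h value is labelled preliminary and comes from the two lowest doses, sampled to 72 h (Section 9.5.1), about two half-lives. Section 5.4.1 speaks of an apparent half-life and a longer terminal phase, which fits a multiphasic profile, and a small slow phase would leave 75 intact. The early-peak statement for telemetry is expressly based on preclinical data, daily ECGs continue to Day 15, and telemetry may be extended or restarted. The SAP (Section 1) records termination after sentinel dosing in Cohort 3, so neither top dose was given.

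Most of this stands, and it limits the point. The cap is not abandoned, and it would be wrong to infer that Part A escalation simply reads its exposures from Table 9. But a future review does not correct a margin that the risk assessment presents as current, and early termination does not make Table 10 right. The small-slow-phase escape exists but is narrow: about 3% of initial concentration for the last-day margin and 5% for the seven-day average.

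**Conclusion.** The point holds for Part B as lack of support for a stated margin. Tables 9 and 10 still reproduce from the 7.8 h parameters, and the reported combination of predicted 24 h exposure with a half-life near 35 h implies lower clearance and accumulation over 7 days. Against the printed 75, plausible values run from about 78 to 36: 44 and 36 in the matched one-compartment case, about 57 at steady state in the tail case. The 177-fold Cmax margin is in doubt for the same reason. All these figures assume linear PK, a 35 h terminal phase, AUC(0-24h) equal to prediction and a back-calculated NOAEL AUC of 1680 µg·h/mL.

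Three stronger readings are not supported:
- That the top Part B regimen has been shown to breach the cap. Half-life alone does not fix AUC, and the documents give no observed clearance.
- That the longer half-life breaks the Part A margin at 54 mg. On the tabulated AUC(0-24h) it does not; what remains there is an AUC(0-∞) value under a 0-24 h heading.
- That margins fall to about 17 or 18. Those figures need V held at 27 L, which contradicts the reported 24 h exposure.

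Earlier protocol versions were not available. That the tables were not updated is inferred from their reproducing from the predicted parameters.

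**What to change.** Recompute and restate, from the PK data already in hand, the exposures and margins in Table 10, in the 54 mg row of Table 9 and in the risk table, giving the clearance, volume and model used. For Part B, show the last infusion day as well as the seven-day average. State which AUC interval the 75-fold cap refers to: first 24 h, any 24 h, seven-day average or 0-∞. Until the restatement is made, describe the Part B margins as predictions from preclinical scaling. Reconcile the early-peak telemetry rationale in Section 2.2, the risk table in Section 3.3.1, Sections 5.4.1 to 5.4.3 and Section 9.3 with one another. This review takes no position on which doses or monitoring rules should follow.

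The cost is one PK re-simulation and text edits, and probably less favourable stated margins.
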